6.2 Primary Efficacy Analysis

The primary endpoint is the proportion of subjects achieving MDA at Week 16. The null hypothesis is that there is no difference in the rate of MDA between the two randomized treatment groups of ADA 40 mg eow + MTX 15 mg ew and MTX 20 - 25 mg or highest tolerable dose ew; the alternative hypothesis is that the rates of MDA between the two groups are different.

Point estimate and 95% CI using normal approximation will be provided for the rate of MDA for each randomized treatment group. Treatment comparisons will be made between the randomized treatment groups using a Cochran-Mantel-Haenszel (CMH)

test^{5,6} (refer to Appendix A), adjusting for the stratification factor which is the duration of prior MTX 15 mg ew use of ≤ 3 months or > 3 months. Point estimate of the treatment difference and the associated 95% CI using normal approximation will also be presented. To account for missing data for the primary endpoint, a non-responder imputation approach (NRI) will be used, e.g., subjects who discontinue during Part 1 with missing data will be imputed as a non-responder (NRI) in the subsequent visits.

Sensitivity analyses will be conducted using the same method described above based on observed cases (OC) data.

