5.2.1 Inclusion Criteria

1. Adult male or female, ≥ 18 years of age at Screening.
2. PsA diagnosis established at least 4 weeks prior to the date of the Screening visit and confirmed by CASPAR criteria at the Screening visit
3. Not in Minimal Disease Activity (MDA) at the time of screening, defined as not meeting at least 5 of the following 7 criteria:
 - Tender joint count (TJC) ≤ 1 out of 68 assessed
 - Swollen joint count (SJC) ≤ 1 out of 66 assessed
 - PASI ≤ 1 or body surface area (BSA) ≤ 3
 - Patient's assessment of pain visual analogue scale (VAS) ≤ 15
 - Patient's global assessment of disease activity (PtGA) VAS ≤ 20
 - HAQ-DI score ≤ 0.5
 - Tender enthesal points ≤ 1 out of 8 assessed
4. Has active arthritis defined as fulfilling both the below criteria at screening and baseline visits:
 - ≥ 3 tender joints (out of 68 assessed)
 - ≥ 3 swollen joints (out of 66 assessed)
5. Treated with MTX 15 mg ew for PsA defined as:
 - Oral or subcutaneous (sc) administration of MTX for at least 4 weeks prior to screening,
 - Change of the MTX administration route (oral or sc) is permitted in this time period if the administered dose of MTX 15 mg ew is not changed,
 - This is the first course of MTX the subject has been receiving for the treatment of PsA,
 - Subject has not received a dosage of MTX higher than 15 mg ew prior to the screening visit,
 - Subject could have been receiving MTX doses lower than 15 mg ew before reaching the stable dose of MTX 15 mg ew defined above,

- If the subject had been on MTX 15 mg ew for ≥ 12 weeks, temporary MTX discontinuation or dose decrease below 15 mg ew for up to 4 weeks is allowed.
6. If subject is receiving concomitant oral corticosteroids, prednisone or equivalent must be ≤ 10 mg/day and the dose must be stable for at least 1 week prior to the Baseline visit
 7. If subject is receiving nonsteroidal anti-inflammatory drugs (NSAIDs), including cyclooxygenase (COX) 2 selective inhibitors, paracetamol (up to the maximum recommended dose in the local country label), the dose must be stable for at least 1 week prior to the Baseline Visit
 8. If subject is receiving other csDMARDs in addition to MTX (i.e., sulfasalazine), the dose must be stable for at least 4 weeks prior to the Baseline visit. If csDMARDs are discontinued before study enrollment, the discontinuation must occur at least 4 weeks prior to the Baseline Visit
 - Leflunomide should be discontinued at least 4 weeks prior to the Baseline visit

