8.1.4 Statistical Analysis of Efficacy

8.1.4.1 Primary Efficacy Variable

The primary endpoint is the proportion of subjects achieving MDA at Week 16 on adalimumab 40 mg eow plus MTX 15 mg ew as compared with subjects on MTX alone escalated to 20-25 mg or highest tolerable dose ew.

The null hypothesis is that there is no difference in response rates between the adalimumab + MTX and MTX groups; the alternative hypothesis is that the response rates between the treatment groups are different. The response rates will be tested using a Cochran-Mantel-Haenszel (CMH) test adjusting for the stratification factor of the duration of prior (to screening) use of MTX at 15 mg ew. The stratification factor is defined as the duration of prior MTX 15 mg ew use of ≤ 3 months or > 3 months.

Sensitivity analyses will be conducted using the same method described above using observed cases (OC).

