4.2 Study Design

4.2.1 Study Design and Design Diagram

This interventional Phase 4 open-label, randomized, controlled, parallel-group, multicenter study will be conducted in two (2) parts, each of 16-week duration.

Part 1 (Day 1 - Week 16) is to compare the achievement of MDA on ADA introduced in combination with MTX versus MTX alone escalated to the highest recommended dose of 20 - 25 mg ew^{1,2} or highest tolerable dose up to 25 mg ew, whatever feasible, in PsA subjects inadequately controlled after the initial course of MTX at 15 mg ew. Part 1 will be open-label, randomized, controlled, parallel group.

Part 2 (Week 16 - 32) is to evaluate the effectiveness of four (4) different treatment regimens consisting of ADA and/or MTX in maintaining or attaining MDA, as applicable.

Part 2 will be open-label, parallel group. Subjects will be assigned into the four treatment arms based on their MDA status at Week 16 and initial randomized treatment. Starting at Week 24, there will be rescue treatment option based on not achieving MDA and investigator's judgment.

The study is designed to enroll approximately 240 subjects at approximately 60 sites to meet scientific and regulatory objectives without enrolling an undue number of subjects in alignment with ethical considerations.

Following a screening period of up to 30 days, subjects meeting the selection criteria will be randomized in a 1:1 ratio to either of the two (2) arms and treated for 16 weeks in Part 1:

- Arm 1/Part 1: ADA 40 mg eow in combination with MTX 15 mg ew (ADA 40 mg eow + MTX 15 mg ew),
- Arm 2/Part 1: MTX escalated to 20 - 25 mg or highest tolerable dose ew (MTX 20 - 25 mg or highest tolerable dose ew).

After the assessment of MDA at Week 16 (primary endpoint), subjects will be assigned to one of the four (4) treatment arms based on the achievement of MDA and initial randomized treatment, and treated for additional 16 weeks in Part 2 as follows:

[figure not shown]
- Arm 1/Part 2: Subjects achieving MDA at Week 16 on ADA 40 mg eow plus MTX 15 mg ew, will have MTX completely withdrawn at Week 16 and continue receiving ADA as monotherapy (ADA 40 mg eow),
- Arm 2/Part 2: Subjects not achieving MDA at Week 16 on ADA 40 mg eow plus MTX 15 mg ew, will have ADA escalated to 40 mg ew in combination with MTX 15 mg ew (ADA 40 mg ew plus MTX 15 mg ew),

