4.4 Sample Size Justification

The study is powered to detect the difference in MDA response rates at Week 16 between ADA + MTX 15 mg and MTX escalated dose groups. Assuming an MDA response rate of 40% in the ADA + MTX group and 20% in the escalated MTX group, a total sample size of 240 subjects, 120 subjects per arm, will provide at least 90% power to detect the difference between the two treatment groups at a significance level of 2-sided 0.05, accounting for 10% dropout.

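### The primary MDA analysis is valid, but it leaves out the number of MDA criteria already met at entry, at a modest cost in precision

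*SAP*

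**What the plan says.** SAP 6.2 compares the randomised groups by CMH, "adjusting for the stratification factor which is the duration of prior MTX 15 mg ew use". Protocol 8.1.4.1 says the same: a "test adjusting for the stratification factor of the duration of prior (to screening) use of MTX at 15 mg ew". The only planned sensitivity analysis repeats this CMH on observed cases. No subgroup in SAP 5.2 or 6.5 uses baseline disease activity.

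MDA means meeting at least 5 of 7 criteria (SAP 4.3.1). Protocol 5.2.1 limits how many a subject may meet at entry:

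- Criterion 3: "Not in Minimal Disease Activity (MDA) at the time of screening, defined as not meeting at least 5 of the following 7 criteria".
- Criterion 4: at least 3 tender and 3 swollen joints at both screening and baseline.

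Protocol Appendix C schedules all seven components at Screening and on Day 1.

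SAP 4.4 sets the trial at 240 subjects, split equally between the arms. It takes MDA rates of 40% on adalimumab and 20% on escalated MTX, and claims that this number "will provide at least 90% power to detect the difference between the two treatment groups". The test level there is two-sided 0.05, and 10% of subjects are expected to drop out.

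**The concern.** Subjects start at different distances from the endpoint. One who meets four criteria at entry and keeps them needs one more at Week 16; one who meets none needs five. The entry count is therefore a partial baseline reading of the endpoint and is likely to predict it. If it does, leaving it out keeps explainable variance in the interval for the MDA difference. An ordinary chance imbalance between arms in the count also stays in the point estimate.

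What is at stake is precision. Planned power sits at the 90% target with nothing in reserve, the data are already being collected, and the trial is open-label. An adjustment chosen after the results are seen would carry little weight.

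**Working it through.** **1. The plan's own power.** Inputs from SAP 4.4 and 4.2.1: 40% vs 20%, 120 per arm, 1:1, two-sided 0.05, 10% dropout. With d the difference and p̄ the mean rate,

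power = Φ{[d√n − 1.96√(2p̄(1−p̄))] / √[p₁(1−p₁) + p₂(1−p₂)]}.

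- n = 120 × 0.9 = 108: (0.20 × 10.392 − 1.96 × 0.6481)/0.6325 = 1.278, power 89.9%. This reproduces the stated 90%.
- Dropouts counted as non-responders (0.40 × 0.9 = 0.36; 0.20 × 0.9 = 0.18; n = 120): (0.18 × 10.954 − 1.96 × 0.6279)/0.6148 = 1.206, power 88.6%.

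Neither figure relies on covariate adjustment.

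**2. Range of the count.** The two joint items need a count of 1 or less, so criterion 4 makes them unmet: 7 − 2 = 5 items remain (skin, pain, PtGA, HAQ-DI, entheses). Criterion 3 caps the total at 4, so the range is 0 to 4 at screening. Criterion 3 is worded for screening, and Appendix C footnote b re-confirms eligibility from Screening-period assessments. Protocol 5.3.1.1 (Randomization) requires subjects still to qualify at Baseline. If criterion 3 is not rechecked, a Day 1 count of 5 is possible.

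**3. Link to Week 16 MDA (assumed).** The documents give no figure. An item-level simulation with assumed item rates and correlations gave control-arm MDA of 7-12% with no item met and 32-55% with four met. As an odds ratio (OR) per item:

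- low: [(0.32/0.68)/(0.12/0.88)]^(1/4) = 3.45^(1/4) = 1.4
- high: [(0.55/0.45)/(0.07/0.93)]^(1/4) = 16.2^(1/4) = 2.0

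**4. Effect of using the count.** Simulation: 6,000 trials per scenario, 108 per arm, 40% vs 20%. Three assumed distributions of 0 to 4 were used: uniform; 10/25/30/25/10%; 40/30/18/9/3%. The planned CMH (two MTX strata) is compared with a CMH also stratified by count (0-1, 2, 3-4). The SE change is √(variance ratio) − 1.

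| OR per item | Variance ratio | SE change | Power, planned | Power, with count |
|---|---|---|---|---|
| 1 | 1.014 to 1.019 | about +1% | 90.1-90.4% | 89.4-90.0% |
| 1.5 | 0.956 to 0.986 | −0.7% to −2.2% | 89.5-90.4% | 90.1-91.5% |
| 2 | 0.890 to 0.920 | −4.1% to −5.7% | 89.0-90.0% | 91.8-92.9% |
| 3 | 0.751 to 0.831 | −8.8% to −13.3% | 89.7-89.9% | 94.9-96.0% |

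The OR 3 row lies outside the range from step 3.

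**5. Standardised risk difference.** With a logistic model instead of extra strata, simulation gives an SE 1-6% lower at OR 1.4-2.0 and an SE ratio of 1.00 at OR 1. To convert this to power at 36% vs 18%, 120 per arm:

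- SE = √(0.36 × 0.64/120 + 0.18 × 0.82/120) = 0.0561; 0.18/0.0561 = 3.207; Φ(3.207 − 1.96) = 89.4%
- SE × 0.99: Φ(3.240 − 1.96) = 90.0%, a gain of 0.6 points
- SE × 0.94: Φ(3.412 − 1.96) = 92.7%, a gain of 3.3 points

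This agrees with the simulated power of about 90-92% for the adjusted test against 88-89% for the CMH, a gain of roughly 0.5-3.5 points. With both rates at 25%, simulated type I error was 5.5% (adjusted) and 5.1% (CMH). The simulation error is √(0.05 × 0.95/6000) = 0.28 points, so 5.5% is within two simulation standard errors of 5%.

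**6. Chance imbalance.** For the 10/25/30/25/10% distribution the SD is √1.3 = 1.14. A two-SE imbalance is 2 × 1.14 × √(2/120) = 0.29 items. At (32 − 12)/4 = 5 to (55 − 7)/4 = 12 MDA points per item, that shifts the difference by about 1.5-3.5 points, against a planned 20.

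**The case against.** The strongest reply is that nothing here is a defect. The CMH adjusts for the only randomisation factor. Randomisation makes it valid, and its test and interval already allow for chance imbalance. That stands.

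The contrast with the continuous endpoints, which are adjusted for baseline, is also weak. The primary endpoint's own baseline value is constant, because nobody is in MDA at screening, and SAP 6.3 treats all binary endpoints alike. The sponsor has also preferred a CMH to a logistic model because the result is reported as a response-rate difference (Protocol 1.1, on the sensitivity analysis). A standardised risk difference respects that preference, so the reason does not exclude it.

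A reader might infer that adjustment would bring power to 92-95%. The documents do not support that. The figure needs baseline covariates with an AUC of 0.70-0.80, which cut the SE by 5-11%. In the item-level simulation the count itself reaches only 0.59-0.70. At AUC 0.64 the SE falls by 2%, and adding the count as CMH strata there changes power by −0.2 to +1.8 points. The higher power also belongs to a test on the adjusted estimate; if the CMH test is kept, its power stays at about 89%. Setting an unadjusted p-value beside an adjusted interval creates a further problem, because the two can disagree near 0.05.

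The objection therefore limits the point to lost precision but does not remove it.

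**Conclusion.** The point holds as a modest loss of efficiency. The omission, the 0 to 4 range at screening and the availability of the data are all plain in the documents. The size is not: it depends on an assumed count distribution and an assumed odds ratio of 1.4-2.0 per item. On those assumptions the SE falls by about 1-6%, and the power of a test based on the adjusted estimate rises by about 0.5-3.5 points. If the count is not prognostic, the logistic approach loses essentially nothing.

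A reader might also infer that the primary result would be biased, or that the trial is underpowered because of this omission. Neither follows. The planned test is valid, and the stated power was never built on covariate adjustment. The 88.6% under non-responder imputation is a separate sample-size matter.

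**What to change.** Before the Part 1 lock, state in SAP 6.2 that the treatment difference and its 95% CI are a standardised risk difference from a logistic model with treatment, randomisation stratum and number of MDA criteria met on Day 1. Use a robust SE and leave non-responder imputation unchanged. Baseline HAQ-DI may be added, but it is already one of the counted items.

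Then choose one of two routes and say which:

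- base the p-value on the same estimate, so that test and interval agree; or
- keep the CMH test as primary, label the adjusted difference as the accompanying estimate, and claim no gain in power.

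The SAP should also allow for a Day 1 count of 5. The cost is a paragraph of wording and one more model to explain. The gain is small if the count predicts weakly.

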6.3 Secondary Efficacy Analyses

Part 1 Analysis

A complete list of secondary efficacy endpoints is provided in Section 4.3.2. Binary endpoints will be analyzed in a similar way as the primary endpoint.

For the continuous endpoints, the change from baseline at Week 16 will be analyzed using MMRM with treatment, the stratification factor of duration of prior MTX use (≤ 3 months or > 3 months), visit, and treatment-by-visit interaction as fixed effects, subject as random effect and baseline measurement as a covariate. The MMRM analysis is based on observed data. The LS mean, 95% CI and standard error for each randomized treatment group, the LS mean of the treatment difference and its associated 95% CI and p-value from the MMRM model will be presented.

Long Term Analysis

The achievement of MDA at Week 32 on each of the four different treatment regimens will be evaluated. The proportion of subjects who achieved MDA at Week 32 will be summarized by counts and percentages for the four treatment regimens. Point estimate and 95% CI using normal approximation will be provided for each treatment regimen as well. The subjects who were rescued prior to Week 32 will be considered as non-

responders (MDA = 0) at Week 32. No comparison between treatment regimens will be performed.

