4.3.2 Secondary Efficacy Endpoints

The secondary efficacy endpoints include:

- At Week 16:
 - Change from baseline in PASDAS
 - Change from baseline in DAPSA score
 - Change from baseline in PsAID score
 - Proportion of subjects achieving ACR 20/50/70 response
 - Change from baseline in DAS28-CRP score

- Proportion of subjects achieving PASI 75/90/100 response (for subjects with BSA \geq 3% at baseline)
- Change from baseline in HAQ-DI score
- Changes from baseline in SF-36PCS and SF-36MCS
- Change from baseline in DLQI score
- Change from baseline in Leeds Enthesitis Index (LEI) (for subjects with presence of enthesitis at baseline)
- Change from baseline in tender dactylitic digit count (for subjects with presence of dactylitis at baseline)
- The proportion of subjects in MDA at Week 32.

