6.0 Efficacy Analyses

6.1 General Considerations

There are two sets of planned efficacy analysis: Part 1 analysis and long-term analysis.

Part 1 Efficacy Analysis

Standard efficacy analysis by the randomized treatment groups (ADA 40 mg eow + MTX 15 mg ew, MTX 20 - 25 mg or highest tolerable dose ew) will be performed on the efficacy data up to Week 16 based on ITT Part 1 population. Formal statistical inference will be generated with missing data handling, and statistical testing will be conducted at $\alpha = 0.05$ level (2-sided). Results from this set of analysis will be used as the key efficacy findings of this study.

No protocol-defined rescue will occur prior to the time point.

Long Term Efficacy Analysis

Long term efficacy analysis from baseline to Week 32 will be performed based on the ITT LT Population by the 4 treatment regimens as described in Section 5.1. Descriptive statistics will be summarized by the four treatment regimens. The between-treatment comparison is not applicable for the long term analysis. No missing data imputation will be performed for long term efficacy analysis.

Rescue handling will be applied for long term efficacy analysis. The data collected after the initiation of the rescue medication will be summarized separately.

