6.4 Other Efficacy Analyses

Clinical Efficacy Variables

Binary secondary endpoints described in Section 4.3.2 will be analyzed as exploratory endpoints at Week 32 using count and percentages on each of the four different treatment regimens. Point estimate and 95% CI using normal approximation will be provided as well. The data occurred after initiation of the rescue medication will be imputed using NRI for the subsequent visits in this summary.

Continuous secondary endpoints described in Section 4.3.2 will be analyzed as exploratory endpoints at Week 32 by summary statistics (number of subjects, mean, 95% confidence interval, standard deviation, median, minimum, maximum) for each treatment regimen. All observed data will be used to summarize the continuous exploratory endpoints. The data occurring after initiation of the rescue medication will be overwritten by the last observation prior to treatment rescue (Last observation carried forward: LOCF) for the subsequent visits in this summary.

Ultrasound Variables

For ultrasound assessment at Week 16, analysis will be performed using similar methods to those described for the secondary continuous efficacy endpoints. In addition, baseline weight will also be included as an additional covariate in MMRM. The LS mean, 95% CI and standard error for each randomized treatment group and the LS mean of the treatment difference, its associated 95% CI and p-values will be presented.

For the ultrasound assessment at Week 32, summary statistics (number of subjects, mean, 95% confidence interval, standard deviation, median, minimum, maximum) will be presented for each treatment regimen. All observed data will be used to summarize the

continuous exploratory endpoints. The data occurring after initiation of the rescue medication will be overwritten by LOCF for the subsequent visits in this summary.

Summary of Efficacy Endpoints by Visit

Summary of the primary and secondary efficacy endpoints at the scheduled time points will be presented by two treatment groups in the Part 1 analysis and by four treatment regimens in the long-term analysis. Achievement of each MDA component as binary endpoints will be summarized similarly as well.

For Part 1 analysis, binary efficacy endpoints will be analyzed in a similar way as the primary endpoint and continuous efficacy endpoints will be analyzed from the same MMRM model for the Wk16 endpoints.

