6.5 Efficacy Subgroup Analyses

The primary efficacy endpoint will be examined in the subgroups listed in [Table 1](#) below. Point estimate of the treatment differences and 95% CI between the randomized treatment groups will be presented for each subgroup. No p-value will be provided for subgroup analysis. If any of the resulting subgroups for a variable has fewer than 20% of the planned study size (i.e., < 48 subjects), the subgroup analyses for that variable will not be presented.

Table 1. Subgroups for Efficacy Analysis

Subgroup Factor	Categories
Age	< 40, [40, 65), ≥ 65
Sex	Male or Female
BMI	< 25 kg/m ² or ≥ 25 kg/m ²
Race	White, Non-white
Geographic region	US, Western Europe/Canada, Eastern Europe/Middle East/Africa, Latin America, Japan/Asia/Pacific
Prior MTX usage	≤ 3 months or > 3 months

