6.6 Efficacy Analysis for Rescued Patients

For the subjects who take at least of one dose of rescue medication, MDA status will be evaluated after rescue at the Week 28 and Week 32. Point estimate and 95% CI using normal approximation will be provided for the response rate of the MDA by 4 treatment regimens as well as overall. The subjects who are rescued at Week 24 and Week 28 will be summarized separately.

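### Normal-approximation intervals for Week 32 and post-rescue response rates under-cover in the smallest groups, chiefly Part 2 Arm 3 (about 22-24 subjects)

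*SAP*

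**What the plan says.** Three SAP sections set the interval method for single-group proportions after Week 16:

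- SAP 6.3, long-term analysis of MDA at Week 32: "95% CI using normal approximation will be provided for each treatment regimen as well". Subjects rescued before Week 32 count as non-responders, and regimens are not compared.
- SAP 6.4, other binary endpoints at Week 32: "Point estimate and 95% CI using normal approximation will be provided as well".
- SAP 6.6, rescued subjects: "Point estimate and 95% CI using normal approximation will be provided for the response rate of the MDA by 4 treatment regimens", and also overall. It adds: "The subjects who are rescued at Week 24 and Week 28 will be summarized separately".

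Neither document names a score, exact or other small-sample interval. Protocol 8.1.4.2 says only that Week 32 MDA is summarised by regimen without testing.

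Other provisions bear on the denominators. SAP 4.3.2 limits the PASI response endpoints to subjects with at least 3% BSA at baseline. SAP 6.1 states: "No missing data imputation will be performed for long term efficacy analysis". SAP 6.5 drops a subgroup variable when any category has "fewer than 20% of the planned study size (i.e., < 48 subjects", but that rule covers only subgroup analyses of the primary endpoint.

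**The concern.** The normal-approximation (Wald) interval is unreliable when the group is small or the proportion is near 0 or 1. Part 2 allocation follows the Week 16 response, so one arm is small by design: Arm 3 contains only those who reach MDA on escalated MTX. Every subject in that arm starts Part 2 in MDA, so a Week 32 proportion well above one half is plausible.

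MDA at Week 32 by regimen is a named secondary endpoint with no between-regimen test. The interval is therefore its stated measure of precision, beside the counts and percentages. If coverage is below the label, the report overstates how well the Arm 3 rate is known, and it may print limits above 100% or intervals of zero width.

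**Working it through.** **Inputs.** SAP 4.4 gives 120 per arm, two-sided 0.05, 10% dropout and the planning rates: "Assuming an MDA response rate of 40% in the ADA + MTX group and 20% in the escalated MTX group".

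**The plan's own figure.** After 10% dropout, n = 120 × 0.90 = 108 per arm. With pooled variance under the null:

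- SE under the null = √(2 × 0.30 × 0.70 / 108) = 0.0624
- SE under the alternative = √((0.40 × 0.60 + 0.20 × 0.80) / 108) = 0.0609
- z = (0.20 − 1.96 × 0.0624) / 0.0609 = 1.28, so power = 89.9%

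Unpooled variance gives 90.8%, so the stated 90% reproduces to within rounding.

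**Expected Part 2 sizes** (rate × 108 to rate × 120):

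- Arm 1: 0.40 × 108 to 120 = 43 to 48
- Arm 2: 0.60 × 108 to 120 = 65 to 72
- Arm 3: 0.20 × 108 to 120 = 22 to 24
- Arm 4: 0.80 × 108 to 120 = 86 to 96

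**Interval formulas**, with p̂ = x/n and z = 1.96:

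- Wald: p̂ ± z√(p̂(1 − p̂)/n)
- Wilson: [p̂ + z²/(2n) ± z√(p̂(1 − p̂)/n + z²/(4n²))] / (1 + z²/n)

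Example, 19/22: p̂ = 0.864 and √(0.864 × 0.136/22) = 0.0732. Wald is 0.864 ± 0.143, or 72.0% to 100.7%. Wilson is 66.7% to 95.3%. For 21/24 the Wald upper limit is also 100.7% (Wilson 95.7%). For 24/24, Wald gives 100% to 100% and Wilson 86.2% to 100%.

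**Coverage.** For a true rate p, exact coverage is the sum of binomial probabilities over every x whose interval contains p. Example, n = 22 and p = 0.85: the Wald interval contains 0.85 only for x = 15 to 20. P(X ≥ 21) = 22 × 0.85²¹ × 0.15 + 0.85²² = 13.7% and P(X ≤ 14) is about 1.1%, so coverage is 85.2%.

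The documents give no Week 32 rates. Averaged over assumed true rates of 60% to 90% in steps of 0.1 points:

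| Arm | n | Wald mean | Wilson mean |
|---|---|---|---|
| 3 | 22-24 | 91.3-91.4% | 95.3% |
| 1 | 43-48 | 93.0-93.1% | 95.1-95.2% |
| 2 | 65-72 | 93.6-93.8% | about 95.1% |
| 4 | 86-96 | 94.0-94.1% | about 95% |

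At 5-point steps within the band, Wald coverage runs from 85.2% to 95.2% in Arm 3 and from 86.4% to 95.2% in Arm 1.

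**Sensitivity of Arm 3 to the assumed rates.** Over 5% to 95%, Wald averages 90.4-90.8%. Over 40% to 70% it averages 92.8-93.0%.

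**Chance that the Arm 3 upper limit exceeds 100%** (n = 22 / n = 24): 6.8% / 4.2% at a true rate of 70%, 32.5% / 25.9% at 80%, and 73.0% / 70.6% at 90%.

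**Illustrations with assumed sizes.** If half of Arm 3 qualified for PASI (n = 11-12), Wald would average 87.0-87.6% over 60% to 90% and Wilson about 96%. For rescue groups with a true rate of 20%, Wald coverage is 66.6% at n = 5, 88.6% at n = 10 and 92.1% at n = 20. A result of 0/5 gives 0% to 0% by Wald and 0% to 43.4% by Wilson.

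**The case against.** The best counter-argument is that little depends on these intervals. SAP 6.1 makes Part 1 the source of the key findings, Part 2 is descriptive, and a reader with the counts can compute any interval. Away from the boundary the methods hardly differ: for 16/24, Wald is 47.8% to 85.5% and Wilson 46.7% to 82.0%. This stands, and it is why the point is minor.

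The 60-90% band is the review's assumption, and scoring rescued subjects as non-responders pulls the rate down. At single points the shortfall vanishes (95.2% at n = 22, p = 0.6). This is fair, but no band restores the nominal level on average: 40-70% still gives about 93%. The chance of a limit above 100% does need high true rates.

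SAP 4.7 treats missing binary data as non-response, whereas SAP 6.1 says nothing is imputed in the long-term analysis. Under SAP 4.7, missing visits would not shrink Arm 3. It would still hold 22-24 subjects, and the coverage figures above use those sizes.

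The PASI and rescue sizes are invented for illustration, and SAP 6.6 does not say whether intervals are printed in each regimen-by-rescue-visit cell. That stands; the case rests on Arm 3.

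The under-48 rule in SAP 6.5 counts both arms, about 24 per arm, so Arm 3 sits near that line. The rule shows only that no small-cell provision reaches Part 2, not that the SAP would regard Arm 3 as too small.

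**Conclusion.** The concern holds, as a minor point. The prescribed interval does not deliver its stated confidence level in Arm 3: average coverage is about 91% for true rates of 60-90% and about 93% for 40-70%, with lower values at some single rates. The effect is mild in Arm 1. It is small in Arms 2 and 4 unless rates are extreme.

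The conclusion assumes that normal approximation means the Wald formula, which is the usual reading since the SAP gives none. It also assumes that Arm 3 comes out near the 20% planning rate; a different Week 16 response would change its size. Shortfalls in PASI and rescue cells are likely wherever those cells are sparse, but they cannot be sized from the documents. The Part 1 primary comparison is not affected.

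**What to change.** In SAP 6.3 (long-term analysis), 6.4 and 6.6, replace the normal-approximation interval for single-group proportions with the Wilson score interval. The Part 1 treatment-difference interval can stay as planned. SAP 6.2 also uses the normal approximation for each Part 1 group, so changing those single-group intervals too would keep Week 16 and Week 32 tables on one method; this is optional.

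The cost is three sentences in the SAP and one option in the SAS procedure. Intervals become asymmetric and sometimes wider. Wilson coverage still dips to about 92% at single points in Arm 3, but it averages about 95%, its limits stay within 0% to 100%, and a 0% or 100% result no longer gets a zero-width interval.
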